3.8.2. Analysis Windows

Subject visits might not occur on protocol-specified days. Therefore, for the purpose of analysis, observations will be assigned to analysis windows. Analysis windows will be calculated relative to study baseline.

Table 3-1. Windows of Time Relative to Study BL Used to Classify Subject Assessments (except DXA, Bone Biochemical Markers and Serology)

Period	Nominal Day	Lowest	Highest
Study BL ^a	1		1
Week 4	28	2	42
Week 12	84	43	126
Week 24	168	127	210
Week 36	252	211	294
Week 48	336	295	378
Week 60	420	379	462
Week 72	504	463	546
Week 84	588	547	630
Week 96	672	631	714
Follow-up Week 24		Last dose date + 155	Last dose date + 182

DXA, BMD, and serum bone biochemical markers data require special consideration, as they are collected infrequently, only at study BL and Weeks 24, 48, 72, and 96 (bone markers data are also collected at the screening visit). Randomization cannot occur until after the BL (pretreatment) DXA scan has been performed. As such, the windowing conventions depicted in [Table 3-2](#) will be used for DXA BMD data.

Table 3-2. DXA BMD and Bone Biochemical Markers Data Windows of Time Relative to Study BL Used to Classify Subject Assessments for Week 96 Analyses

Period	Nominal Day	Lowest	Highest
Study BL ^a	1		1
Week 24	168	2	252
Week 48	336	253	420
Week 72	504	421	588
Week 96	672	589	756

^a Study day computed from first dose date of TDF.

Windowing conventions to be used for serology data relative to study baseline are depicted in [Table 3-3](#).

Table 3-3. Serology Data Windows of Time Relative to Study BL Used to Classify Subject Assessments

Period	Nominal Day	Lowest	Highest
Study BL	1		1
Week 24	168	2	252
Week 48	336	253	420
Week 72	504	421	588
Week 96	672	589	756 *

a Study day computed from first dose date of TDF.

3.8.3. Selection of Data in the Event of Multiple Records in a Window

Depending on the statistical analysis method, single values may be required for each analysis window. For example, change from baseline by visit usually requires a single value, whereas a time-to-event analysis would not require one value per analysis window. When a single value is needed, the following rule(s) will be used:

Serology

In the event that 2 or more serology results (eg, HBeAg and anti-HBe or HBsAg and anti-HBs) occur within the same visit window, then the pair will remain together and the last pair of results in the window will be used for analysis purposes.

ALT

The highest value will be included in the analysis when 2 or more ALT values occur within the same visit window.

HBV DNA values (log₁₀ copies/mL)

- 1) Select the record closest to the nominal day (eg, Day 168 for analysis Week 24) for that visit.
- 2) If there are 2 visits equidistant from the nominal day, take the latest.
- 3) If there are multiple records on a selected day, take the geometric mean. If there are 2 values on the same day and it can be determined that the second one is a retest because there was a problem with the first test (for example, specimen hemolyzed), in these cases, the later value should be used.

All other laboratory parameters, DXA data, height, weight, and BMI

- 1) Select the record closest to the nominal day (eg, Day 168 for analysis Week 24) for that visit.
- 2) If there are 2 visits equidistant from the nominal day, take the latest.
- 3) For continuous variables, if there are multiple records on a selected day, take the arithmetic mean. For laboratory parameters, if there are 2 values on the same day and it can be determined that the second is a retest because there was a problem with the first test (for example, specimen hemolyzed), then the later value will be used. For categorical variables, if there are multiple records on a selected day, take the later value.

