Screening measures for Monitoring Groups 1 and 2 will include determining a subject's eligibility into the study with the following criteria: current age, documentation of chronic HBV infection, prior Tenofovir DF exposure, weight, laboratory assessments, ability to swallow solid tablets, subject's ability to adhere to treatment regimen, obtaining written informed consent from subject's parent or legal guardian or obtain informed assent from the subject

Baseline measures for Monitoring Groups 1 and 2 will include laboratory assessments for HBV DNA, HBV serology, HCV, HDV, and HIV polymerase chain reaction (PCR) testing, HBV genotyping, serum renal and bone chemistries, liver function, hematology, urinalysis. DEXA imaging, a physical exam (including pregnancy testing for females), current concomitant medications and any reported prior bone and renal AEs, will also be collected.

FREQUENCY OF STUDY PROCEDURES ([Appendix 2](#)):

Subjects enrolled to either Group 1 or 2 will have the following measures assessed:

- HBV DNA: every 12 weeks
- HBV serology: every 24 weeks
- Liver chemistry (i.e., alanine aminotransferase (ALT), alkaline phosphatase (ALP), aspartate aminotransferase (AST), total and direct bilirubin, total protein, albumin, gamma glutamyl transpeptidase (GGT), lactate dehydrogenase (LDH), creatine kinase (CK) every 24 weeks
- Hematology (i.e., complete blood count with differential and platelets, PT/INR): every 24 weeks
- Physical Examination and Drug Dispensing: every 12 weeks
- Documentation of bone or renal AEs since the subject's last visit
- Documentation of medical management in the event of bone or renal AEs

Subjects enrolled to Group 1 will have the following additional monitoring;

- DEXA: every 24 weeks from Baseline to Week 96 (5 scans)
- Serum bone chemistry (i.e., calcium, phosphorus, vitamin D levels (25-hydroxy and 1, 25 dihydroxyvitamin), parathyroid hormone (PTH), osteocalcin, bone-specific alkaline phosphatase, N and C telopeptides): every 24 weeks
- Serum renal chemistry (i.e., glucose, creatinine, calculated creatinine clearance, magnesium, bicarbonate, chloride, potassium, sodium): at 4 weeks and 12 weeks from Baseline and every 12 weeks thereafter, according to SmPC
- Urinalysis (i.e., protein, glucose, creatinine, phosphate, bicarbonate, blood, calcium): at 4 weeks and 12 weeks from Baseline and every 12 weeks thereafter

Subjects enrolled to Group 2 will have the following monitoring:

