- DEXA: every 48 weeks from Baseline to Week 96 (3 scans)
- Serum bone chemistry (i.e., calcium, phosphorus, vitamin D levels (25-hydroxy and 1,25 dihydroxyvitamin), PTH, osteocalcin, bone-specific alkaline phosphatase, N and C telopeptides): every 48 weeks
- Serum renal chemistry and urinalysis according to local standards of care

Subjects who permanently discontinue Tenofovir DF will be asked to return for an end of treatment visit within 72 hours of the last dose of Tenofovir DF. Subjects who permanently discontinue Tenofovir DF will be followed for 24 weeks off treatment or up to initiation of local standard of care treatment, whichever occurs first.

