1.4. Sample Size and Power

Planned Sample Size	100 subjects (50 subjects to one of two monitoring groups)
Power Statement	
The study employed two monitoring protocols which specified the same laboratory and imaging tests for bone and renal markers and differed in the frequency of testing. Group 1 receives more frequent monitoring which is protocol-defined or SmPC specified, and Group 2 subjects are monitored according to a less frequent DXA schedule for BMD and followed the local standard of care for renal monitoring. It is hypothesized (H_0) that there would have been no difference in the timing, management, or subject outcomes resulting from renal or bone AEs among the two monitoring regimens. With a one-tailed test of $\alpha=0.05$, and assuming a non-inferiority margin of 0.10, the study had at least 80% power to detect a difference between the monitoring regimens beyond the specified margin of non-inferiority.
 
The primary safety endpoint is cumulative incidence of at least a 4% decrease from study baseline (BL) in spine bone mineral density (BMD) through Week 96.
 
The null hypothesis is the difference (Group 1 – Group 2) is equal to 0.
 
The alternative hypothesis is the difference (Group 1 – Group 2) is not equal to 0.

Actual Enrollment and Impact on Power	
The study failed to achieve its targeted enrollment of 100 patients, 50 per monitoring group. The study was discontinued as a result of the recent approval of Tenofovir alafenamide fumarate (TAF) medicine which offers a safer treatment option for CHB patients and due to low subject enrollment after the CHMPs assessment of the 18 month interim enrollment report. At the time of its closure the study enrolled 30 patients, 15 per monitoring group. The total enrolled subjects are underpowered to statistically detect differences in outcomes between monitoring groups.

--	--

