2. TYPE OF PLANNED ANALYSIS

2.1. Final Analysis

Final Analysis includes the time period from the first date of OL TDF dose through and including the date of last OL TDF dose plus 30 days. As a result of early study termination (FPFV July 2015 to LPLV April 2018) only two patients completed 96 weeks of observation on TDF treatment for HBV, the primary study objective to characterize the safety profile (renal and bone adverse outcomes) of subjects will be summarized based on available TDF exposure time. The assessment of efficacy and tolerability of TDF will be described. As most of the enrolled subjects were unable to complete the target observation period of 96 weeks, the final analysis will be unable to provide meaningful evidence to suggest whether enhanced or standard of care renal and bone monitoring frequencies between Group 1 and Group 2 offer early detection and mitigation of renal or bone adverse events. Instead, the data will be described by monitoring group and pooled together where possible.

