4.2. Disposition of Subjects

A summary of subject disposition will be provided by monitoring group and overall. This summary will present the number of subjects screened, randomized, included in the safety analysis set, and the number and percentage of subjects meeting the following criteria:

- Completed the study treatment period,
- Did not complete the study treatment period (with summary of reasons for not completing the study treatment period),
- Completed the study (includes the study treatment period), and
- Did not complete the study (with summary of reasons for not completing the study).

The denominator for the percentages of subjects in each category will be the number of subjects in the Safety Analysis set.

No inferential statistics will be generated. A data listing of reasons for premature study treatment/study discontinuation will be provided. The most recent, non-missing primary and key secondary endpoint values prior to discontinuation will be included in this listing.

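### BMD is tabulated by nominal study week only, with no early-exit or last on-treatment DXA row, although 28 of 30 subjects did not complete 96 weeks

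*SAP*

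**What the plan says.** **Windows.** SAP 3.8.2 states that "Analysis windows will be calculated relative to study baseline". Table 3-2, titled "DXA BMD and Bone Biochemical Markers Data Windows of Time Relative to Study BL Used to Classify Subject Assessments for Week 96 Analyses", gives Week 24 = Days 2-252, Week 48 = 253-420, Week 72 = 421-588 and Week 96 = 589-756. One set serves both monitoring groups. It has no row for an early-exit or last on-treatment scan.

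**Selection.** When a single value per window is needed, SAP 3.8.3 instructs for DXA: "Select the record closest to the nominal day (eg, Day 168 for analysis Week 24) for that visit". The later scan is taken only if two are equidistant. The same section notes that time-to-event analyses do not need one value per window.

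**Display.** SAP 7.3 and Tables 26.1-26.3 and 27.1-27.3 present BMD by study week.

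**What happened.** SAP 1.4: "At the time of its closure the study enrolled 30 patients, 15 per monitoring group". SAP 2.1: "only two patients completed 96 weeks of observation on TDF treatment for HBV". SAP 2.1 and 7.8 say that the safety summary will rest on the TDF exposure that is available. For efficacy, SAP 6.3 accordingly admits the early discontinuation visit in place of Week 96. SAP 7.3 has no counterpart for BMD. SAP 4.2 gives a listing of discontinuations: "The most recent, non-missing primary and key secondary endpoint values prior to discontinuation will be included in this listing".

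**Schedule.** Group 1 is scanned at Baseline and Weeks 24, 48, 72 and 96; Group 2 at Baseline and Weeks 48 and 96 (Protocol 3.2).

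**The concern.** The windows and the selection rule were built for subjects who attend on schedule to Week 96. Almost nobody did. Where a scan was done at exit, it carries that subject's longest TDF exposure and is the most informative observation for a long-term bone safety objective.

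The by-week tables can treat such a scan poorly in two ways. They can label it with a week far from the exposure it represents, so that a scan after a few weeks of TDF sits in the Week 24 column. They can also leave it out, because a scheduled scan in the same window lies closer to the nominal day. What is at stake is whether a reader of the BMD tables can tell how much exposure stands behind each figure, and whether the longest-exposure scan is counted at all.

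**Working it through.** **Inputs.** Enrolled 30, 15 per group (SAP 1.4); completers 2 (SAP 2.1); windows and nominal days 168, 336, 504, 672 (SAP Table 3-2); selection rule (SAP 3.8.3); scan schedules (Protocol 3.2); exit paragraphs (Protocol 6.4.2-6.4.6). Not given: exit days and the number of exit scans.

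**Reproducing the plan's figures.** Midpoints between successive nominal days are (168+336)/2 = 252, (336+504)/2 = 420 and (504+672)/2 = 588; the last bound is 672+84 = 756. All four agree with Table 3-2. Non-completers: 30 - 2 = 28, or 28/30 = 93.3%. Days 2-756 are covered without a gap, so the windows alone drop nothing. A scan is lost only when another scan in its window is closer to nominal.

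**When is an exit scan taken?** The protocol can be read in two ways.

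- *Next-visit reading.* Each visit section has its own early-exit paragraph. The sets for Weeks 12/36 and 60/84 contain no DXA, the Week 24/72 set has it for Group 1 only, and the Week 48 and Week 96 sets have it for both groups.
- *Week 96 reading.* The paragraph in 6.4.6, taken literally, requires all Week 96 assessments, DXA included, from anyone who leaves before Week 96.

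I classified each possible exit day from 2 to 671 (670 days), with scheduled scans placed on their nominal days.

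**Next-visit reading.**
- Group 1 exit scans fall on Days 85-167, 253-335, 421-503 and 589-671: 4 × 83 = 332 days. Group 2: 253-335 and 589-671, 2 × 83 = 166 days.
- None is dropped, because the scheduled scan for that window has not yet been done.
- Largest mislabel: 168 - 85 = 83 days early.
- More than 14 days from nominal, the protocol's DXA tolerance: 276/332 = 83% in Group 1 and 138/166 = 83% in Group 2.

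**Week 96 reading.**
- Largest mislabel: 168 - 2 = 166 days early.
- Dropped in Group 1: Days 169-252, 337-420 and 505-588, 3 × 84 = 252; 252/670 = 37.6%.
- Dropped in Group 2: Days 337-420 only; 84/670 = 12.5%.
- With scheduled scans shifted at random by up to ±14 days, a simulation gives 34.3% and 11.5%.
- Group 2 exit days labelled Week 24 or Week 72, where that group has no planned scan: 251 + 168 = 419; 419/670 = 62.5%.
- Example: an exit scan on Day 240 is dropped in Group 1, where the Day 168 scan wins, but becomes Week 24 in Group 2.

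**In subjects (Week 96 reading).** Assume 28/2 = 14 early exits per group (13 to 15 are possible). Uniform exit over Days 2-671 gives about 14 × 0.376 = 5.3 scans dropped in Group 1 and 14 × 0.125 = 1.8 in Group 2. Other assumed exit ranges give 3.5 to 9.4 and 0 to 4.7. Under the next-visit reading both are zero.

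**The case against.** Several points on the other side stand.

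- **The dropping depends on one reading of the protocol.** Under the next-visit reading no exit scan is lost, a Group 1 exit on Day 240 has no scan at all, and mislabelling is equally frequent in the two groups.
- **The primary safety endpoint may be spared.** Protocol 8.6.4 specifies time-to-event methodology for the decrease of at least 4%, and SAP 3.8.3 exempts such analyses from the one-value rule. SAP 7.3 does not repeat that method and asks for results by study week, so Tables 26.1 and 27.1 are neither clearly safe nor clearly affected.
- **The last value is not lost to the report.** The SAP 4.2 listing shows it and is readable for 30 subjects. It gives no summary by group or pooled.
- **The consequences are bounded.** On the nominal schedule a dropped scan is at most 84 days later than the one kept, and the subject stays in that column. SAP 7.3 computes no inferential statistics for BMD, and SAP 2.1 disclaims a meaningful group comparison.

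A reader might go further and infer that the rule biases the Group 1 versus Group 2 comparison about threefold. The documents do not support that. The ratio is a share of hypothetical days under one reading and an assumed uniform exit pattern. The sponsor closed the study, so exit days depend on enrolment dates that are not reported, and no planned BMD test would be affected.

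A reader might also want to narrow the windows, say to ±6 weeks. Under the Week 96 reading, 247/670 = 37% of exit days in Group 1 and 331/670 = 49% in Group 2 give a kept scan more than 42 days from nominal. All of these would leave the by-week columns, unequally by group. If Tables 26.1 and 27.1 use the same windows, a loss of 4% or more seen at exit could disappear from them.

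**Conclusion.** The point holds as a reporting defect worth correcting. BMD is shown by nominal week only, in a study where 28 of 30 subjects stopped short and the SAP itself undertakes to summarise by available exposure. Efficacy was adapted to early exit; BMD was not.

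Mislabelling follows under either reading of the protocol: up to 83 days under the next-visit reading, up to 166 days under the Week 96 reading. Omission from the by-week percent-change and Z-score tables, and its greater frequency in Group 1, arise only under the Week 96 reading. The figures of 38% and 12.5% further assume that every early exit is scanned, that scheduled scans fall on nominal days and that exits are uniform over Days 2-671. They show that the effect can be unequal; they do not measure it.

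**What to change.** - **Keep the Table 3-2 windows as they are.**
- **Add a last on-treatment DXA row** to Tables 26.2, 26.3, 27.2 and 27.3, by group and pooled, giving percent change, Z-score change and weeks of TDF at that scan. Define on-treatment explicitly. The SAP 2.1 period, last dose plus 30 days, would include an exit visit made within 72 hours of the last dose.
- **State in SAP 7.3** that Tables 26.1 and 27.1 use all on-treatment scans at their actual study day, in line with Protocol 8.6.4.
- **Reconcile the exit paragraphs in Protocol 6.4.2-6.4.6** on when an exit DXA is taken, and record the outcome in the SAP so that the origin of exit scans is clear.

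The row enters every exit scan under either reading and needs no new data. The cost is SAP wording and a little programming. Its drawback is that it mixes exposure durations, so weeks of TDF must be shown beside it.

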3.9. Handling Missing Data in Evaluation of Efficacy

3.9.1. Missing = Excluded Analysis

The primary method of handling missing data in evaluation of efficacy is the missing = excluded (M = E) approach. Due to the ad-hoc nature visits and tests within study group 2, M=E is preferred.

3.9.2. Missing = Failure Analysis

An alternative to the M = E approach is the missing = excluded (M = F) approach.

4. SUBJECT DISPOSITION

4.1. Subject Enrollment

The number and percentage of subjects screened (without percentage), randomized, randomized and treated with TDF, randomized and treated with TDF for all countries combined and by country and investigator site will be summarized by monitoring group and overall. Similarly, the number and percentage of subjects randomized into each age group (12-14 years, 15–16 years) and geographic region (by EU members) will be summarized. The denominator for this calculation will be the number of subjects in the Randomized Analysis Set.

4.2. Disposition of Subjects

A summary of subject disposition will be provided by monitoring group and overall. This summary will present the number of subjects screened, randomized, included in the safety analysis set, and the number and percentage of subjects meeting the following criteria:

- Completed the study treatment period,
- Did not complete the study treatment period (with summary of reasons for not completing the study treatment period),
- Completed the study (includes the study treatment period), and
- Did not complete the study (with summary of reasons for not completing the study).

The denominator for the percentages of subjects in each category will be the number of subjects in the Safety Analysis set.

No inferential statistics will be generated. A data listing of reasons for premature study treatment/study discontinuation will be provided. The most recent, non-missing primary and key secondary endpoint values prior to discontinuation will be included in this listing.

4.3. Extent of Exposure

4.3.1. Duration of Exposure to TDF

Duration of exposure to TDF will be defined as $(\text{last dose date} - \text{first dose date} + 1)/7$, regardless of temporary interruptions in TDF administration, and will be expressed in weeks (recorded to one decimal place, e.g., 4.5 weeks). Duration of exposure to TDF will be summarized using descriptive statistics (sample size, mean, standard deviation, median, first quartile (Q1), third quartile (Q3), minimum and maximum) and as the number and percentage of subjects with data in a given analysis window (using the analysis windows defined in Section 3.8.2) by monitoring group and overall for the Safety Analysis set. No inferential statistics will be computed.

4.3.2. Adherence with TDF

Descriptive statistics for adherence (sample size, mean, standard deviation, median, Q1, Q3, minimum and maximum) along with the number and percentage of subjects belonging to adherence categories (e.g., < 80%, ≥ 80 to < 90%, ≥ 90%) will be provided by monitoring group for the safety analysis set. No inferential statistics will be provided.

For the Final Analyses:

Adherence (%) with TDF during the treatment period will be calculated as where

$$\text{Adherence (\%)} = 100 \times \frac{\sum \text{Number of tablets taken at each distinct dispensed period [1]}}{\sum \text{Number of tablets prescribed at each distinct dispensed period [2]}}$$

[1] Number of tablets taken at each distinct dispensed period is calculated as the minimum of [the daily number of pills prescribed multiplied by the duration of treatment* at each dispensed period of the same dispensed date, and (number of pills dispensed minus the number of pills returned)].

[2] Number of pills prescribed at each distinct dispensed period is calculated as the daily number of pills prescribed multiplied by the duration of treatment* at each dispensed period of the same dispensed date.

* The duration of treatment at each dispensed date is calculated as the minimum of (the last returned date of the same dispensed period, date of last pill of permanent discontinuation of study regimen, and next pill dispensed date) minus dispensed date.

The next pill dispensed date is the following dispensed date of the same drug, including the TDF bottle not returned.

Adherence will be calculated and summarized for each subject for the entire dosing period up to the date of permanent discontinuation of the study regimen.

For a record where the number of pills returned is missing, it is assumed the number of pills returned is 0. If the number of pills dispensed is missing, then all records for the same dispensed date will be excluded from both denominator and numerator calculation.

If any TDF bottle is not returned for the same dispensed date, then all of the records for the dispensed date will be excluded from both denominator and numerator calculation.

In case of any additional bottles dispensed to cover a longer than protocol-specified-visit period, these extra bottles will be counted in the calculation.

Adherence will be calculated and summarized for TDF tablets for each subject for the entire dosing period. Treatment interruptions approved by the investigator are not considered to be non-adherence.

Descriptive statistics for adherence (sample size, mean, standard deviation, median, Q1, Q3, minimum and maximum) along with the number and percentage of subjects belonging to adherence categories (eg, $< 90\%$, $\geq 90\%$) will be provided by monitoring group and overall. No inferential statistics will be computed.

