5.3. Dosage and Administration of Tenofovir DF

Subjects will be assigned to receive one of the following treatments in an unblinded fashion:

Group 1: open-label Tenofovir DF 300mg PO once daily, enhanced monitoring

Group 2: open-label Tenofovir DF 300mg PO once daily, Tenofovir DF, local standards of care for monitoring

Subjects will be instructed to take one tablet by mouth daily. Tenofovir DF should be taken with food.

After 96 weeks of protocol-guided monitoring, each subject will switch to medical management for CHB as per local standards of care.

Active study subjects will be dispensed Tenofovir DF at baseline and through the end of the study (until each subject reaches Week 96). Subjects will be instructed to return empty containers as well as unused study medication in the original container at each study visit. The investigator will be responsible for maintaining accurate records for Tenofovir DF and Tenofovir DF bottles dispensed and returned. The inventory must be available for inspection by the study monitor. Study medication supplies, including partially used or empty bottles, must be accounted for and the dispensing logs must be verified by the study monitor prior to destruction or return.

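### The adherence formula in SAP 4.3.2 does not carry out its own rule on approved interruptions, and scoring a missing return count as zero pushes adherence upward

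*SAP*

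**What the plan says.** SAP 4.3.2 (Adherence with TDF) defines adherence as 100 times the sum of tablets taken divided by the sum of tablets prescribed, over dispensing periods.

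- **Prescribed:** "Number of pills prescribed at each distinct dispensed period is calculated as the daily number of pills prescribed multiplied by the duration of treatment".
- **Taken:** the smaller of that same product and the "number of pills dispensed minus the number of pills returned".
- **Duration:** the dispensing date is subtracted from the earliest of three dates. One is the last return date. The other two are the "date of last pill of permanent discontinuation of study regimen, and next pill dispensed date) minus dispensed date".

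The section then adds four rules:

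- Missing return count: "For a record where the number of pills returned is missing, it is assumed the number of pills returned is 0".
- Missing dispensed count: "If the number of pills dispensed is missing, then all records for the same dispensed date will be excluded".
- Unreturned bottle: "If any TDF bottle is not returned for the same dispensed date, then all of the records for the dispensed date will be excluded".
- Approved holds: "Treatment interruptions approved by the investigator are not considered to be non-adherence".

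The section gives adherence categories twice, each time as an example: first three levels cut at 80% and 90%, later two levels cut at 90%.

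**The concern.** Two things do not fit together.

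First, the sentence on approved interruptions states a result that the formula does not produce. The duration is calendar time, and only a return, a permanent stop or a new dispensing ends it. A temporary hold with the bottles still at home adds days to the denominator and nothing to the numerator. The protocol foresees holds (sections 7.5.2 and 7.5.4), so the case can occur.

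Second, three gaps in the drug accounts are handled in two ways. A missing dispensed count and an unreturned bottle remove the dispensing date. A missing return count is filled in with the value most favourable to adherence, although SAP 3.6 says that missing data are in general not imputed.

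At stake is the accuracy of the adherence summary by monitoring group. Adherence is listed within the secondary endpoints (Protocol 3.1 and 8.1.3). Exposure duration in SAP 4.3.1 ignores temporary interruptions, so adherence is the planned summary that describes actual tablet intake. The two errors run in opposite directions, so the net bias cannot be signed in advance. If Group 1's closer renal testing led to more holds, the interruption error would also fall unequally on the groups.

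**Working it through.** The plan states no adherence value, so there is no figure to reproduce. The formula is applied as written.

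**Inputs**

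- Daily tablets: 1 (Protocol 5.3: "Subjects will be instructed to take one tablet by mouth daily").
- Period: 84 days, the regular 12-week interval. Eight periods make 672 days. The extra Week 4 dispensing in Group 1 is ignored for simplicity.
- Supply: 30 tablets per bottle and enough for 12 weeks (Protocol 5.2.2). Assumed to be 3 bottles, or 90 tablets.
- Visit window: ±7 days, so two 12-weekly visits can lie up to 84 + 14 = 98 days apart.
- Hold: 14 days as an example, from the two-week follow-up in Protocol 7.5.4.

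**Formula per period:** taken = min(1 × duration, dispensed − returned); prescribed = 1 × duration.

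**A. Approved hold, bottles not returned, otherwise perfect intake**

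The subject takes 84 − 14 = 70 tablets and returns 20. Taken = min(84, 90 − 20) = 70; prescribed = 84; score = 70/84 = 83.3%. Under the SAP's own sentence it should be 100%.

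| Total days | Score with one 14-day hold | Hold length beyond which the score is below 90% |
|---|---|---|
| 84 | 70/84 = 83.3% | 8.4 days |
| 168 | 154/168 = 91.7% | 16.8 days |
| 336 | 322/336 = 95.8% | 33.6 days |
| 672 | 658/672 = 97.9% | 67.2 days |

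The shorter the follow-up, the larger the effect. By SAP 2.1, two subjects reached 96 weeks.

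**B. Missing return count**

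- All counts for the date missing: taken = min(84, 90 − 0) = 84, score 84/84 = 100%. This is the same whether 0, 21, 42 or 63 tablets were really taken (true 0%, 25%, 50%, 75%). Even a perfect taker would return 90 − 84 = 6 tablets, not 0.
- Supply shorter than the period: 90/91 = 98.9% at 91 days and 90/98 = 91.8% at 98 days, unless extra bottles were dispensed.
- One of three bottle counts missing: true returns 0, 10 and 20 give (90 − 30)/84 = 71.4%. If the 10 is missing, the score is (90 − 20)/84 = 83.3%, so it is raised but not to 100%.

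Over eight periods for a subject truly at 63/84 = 75%, with k periods fully missing, the score is [84k + 63(8 − k)]/672:

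| k | Score under the SAP rule | Score with those dates excluded |
|---|---|---|
| 1 | 525/672 = 78.1% | 75.0% |
| 2 | 546/672 = 81.3% | 75.0% |
| 4 | 588/672 = 87.5% | 75.0% |
| 5 | 609/672 = 90.6% | 75.0% |

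Two missing counts carry the subject over the 80% cut, and five over the 90% cut.

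**C. Both together:** a period with a 14-day hold and all return counts missing scores 100%. The second rule hides the first problem.

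**The case against.** A reader might infer that adherence is the exposure measure behind the bone, renal and virological results, so that these are biased too. The documents do not support that. SAP 4.3.1 defines exposure from first and last dose dates, SAP 2.1 and 7.8 base the final safety analysis on available exposure time, and Protocol 8.1.3 bases incidence rates on cumulative exposure. No analysis set, covariate or denominator for bone density, laboratory, adverse event or efficacy results uses adherence. It feeds one table (Table 7 in SAP Appendix 3), without tests. This objection stands in full.

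A reader might also infer that every missing count yields 100%. It does not: the rule works per record, and 100% needs all counts for the date to be missing and the supply to cover the period. Partial cases are biased by less, but still upward.

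A missing count may belong to a bottle that came back empty, since unreturned bottles are excluded and Protocol 5.3 asks for empty containers. Zero is then correct, and excluding the date would discard good adherence. Protocol 5.6 also requires returned quantities to be recorded, so missing counts should be few. This is a fair limit, and the remedy has to allow for documented empty bottles. It does not justify assuming that every missing count means an empty bottle.

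On interruptions, the daily number prescribed could be read as zero during a hold, and if drug is returned at the hold and re-dispensed at restart, the gap drops out through the return date. Both are possible. The SAP states neither reading, and the penalty remains when the bottles stay out, so the programmer has to guess.

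**Conclusion.** The point holds, with limited reach. As written, the formula contradicts the section's rule on approved interruptions whenever the bottles stay dispensed: 83.3% instead of 100% for a 14-day hold in 84 days, shrinking to 97.9% over 672 days. The missing-count rule raises adherence, to 100% for the period under the two conditions above and by less otherwise, while neighbouring gaps are excluded.

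The sizes rest on one tablet daily, 90 tablets per 84 days, equal periods and, for the eight-period example, a true adherence of 75%, which is an illustration. How often counts were missing or treatment was held is not given, so the real bias is unknown. The effect is confined to the descriptive adherence summary. Reading it as a threat to the bone density, renal, adverse event or virological analyses would go beyond the documents. It is a low-priority correction.

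**What to change.** Three edits to SAP 4.3.2:

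1. Define prescribed tablets as the daily number × (duration − approved interruption days falling within that duration), and use the same quantity as the cap on tablets taken. Changing only the denominator would let a score exceed 100%. In the example, min(70, 70)/70 = 100%.
2. Exclude a dispensing date with a missing return count from numerator and denominator, as is already done for a missing dispensed count, unless the bottle is documented as returned empty, when zero is used. Report the number of dates excluded by monitoring group.
3. State one set of adherence categories in both places.

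The cost is a few sentences and minor programming. Listings of drug administration and accountability (Listings 12 and 13 in SAP Appendix 3) are already planned; it is assumed that hold dates and the investigator's approval can be identified from the collected data. The downside is that some periods drop out, and with short follow-up a subject with few periods may have no adherence value.
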